This study employs an **experimental research design** utilizing **randomized assignment** and **repeated measures**. Participants who consent to the study will be allocated to either the experimental group (Group A) or the control group (Group B). Group A participants will listen to self-selected music in addition to receiving standard care. Group B participants will receive standard care only. The objective is to evaluate the effectiveness of music therapy in alleviating fatigue. A total of 44 patients with leukemia undergoing their initial chemotherapy will be recruited, with 22 participants allocated to each group.

The measurement process will be conducted in two parts:

1. **Primary Data Collection:** Data will be collected at two main time points: upon admission for initial chemotherapy (Baseline, T0) and on Day 21 of the

chemotherapy cycle (T1). On Day 21, the researcher will visit the ward to collect the required data, including the Tang's Fatigue Scale, the Fatigue Numerical Rating Scale (NRS), and clinical laboratory data. If a participant has been discharged, data will be collected via telephone interview or an online questionnaire.

2. **Symptom Diary:** Participants will record their fatigue levels using the Fatigue NRS immediately following each music therapy session.

Baseline demographic data will be collected only at T0. The measurement time points and the application of corresponding instruments are detailed in Table 3-2.

Table 1: Schedule of Research Measurements

Time	Before Chemo (T0)	Chemo Day 7	Chemo Day 14	Chemo Day 21 (T1)
Tang's Fatigue Scale	○			○
Numerical Rating Scale (NRS)	○	○	○	○
WBC	○			○
Hemoglobin	○			○
Albumin	○			○
Demographic Data	○			

Note: ○ = Data to be collected

Research Setting and Participants

This study will be conducted in the hematology-oncology ward of a medical center located in Northern Taiwan. Participants must meet the following inclusion criteria:

1. Clinically diagnosed with Acute Myeloid Leukemia (AML) by a specialist physician.
2. Scheduled to receive initial (first-time) chemotherapy.
3. Aged 20 years or older.
4. Able to communicate in Mandarin or Taiwanese.
5. Possess normal hearing ability.
6. No history of psychiatric illness and clear consciousness.
7. No prior participation in any fatigue management intervention study.
8. Understands the research purpose, voluntarily agrees to participate, and has signed the informed consent form.

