9. Willing to cooperate with all study procedures during the research period.

Participants will be **excluded** from the study if they meet the following criteria:

1. Severe hearing impairment.

2. Unstable vital signs or unclear consciousness.

III: Sample Size Calculation

The sample size was estimated based on the **Generalized Estimating Equations (GEE)** approach for repeated measures. The analysis will control for baseline demographic and disease characteristics as covariates (e.g., age, sex, education level, occupation, perceived economic status, marital status, religious beliefs, and metastasis). The dependent variables are fatigue, White Blood Cell (WBC) count, hemoglobin, and albumin.

The calculation was performed using G*Power software (version 3.1.9.7). Parameters were set as follows: a significance level (α) of 0.05, statistical power ($1-\beta$) of 0.80, a 95% confidence interval, and an anticipated **effect size of 0.21**. This calculation yielded a required sample size of 34 participants (as shown in Figure 3-2). To account for a potential attrition rate of 30%, the study aims to recruit a total of **44 participants** ($n=22$ for Group A, $n=22$ for Group B).

Music Therapy Protocol

1. Music Selection, Dosage, and Headphone Use

According to the literature, a music therapy duration of 15–30 minutes is effective for fatigue alleviation (Burns et al., 2008; Cassileth et al., 2003; Miladinia et al., 2021; Reimnitz et al., 2020; Sezgin & Bektas, 2022). Music selection will be based on individual preferences and cultural background (Tsai & Chou, 2015; Browning, 2000; Gerdner, 2000).

To ensure data integrity while considering the patient's length of stay, physical burden during chemotherapy, and protocol adherence, the music therapy intervention in this study will be administered **once daily for 21 consecutive days**. The **30-minute intervention** will commence at the start of the chemotherapy infusion. During the study, participants will be provided with a chemotherapy symptom tracking diary to confirm adherence to the music therapy protocol in the experimental group.

For reasons of personal hygiene, preference, and potential patient discharge, participants will be asked to use their own headphones. If a participant does not have headphones, a set will be provided by the researcher.

Research Instruments and Psychometric Properties

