1. Participant Demographic Data Sheet Data will be collected using Google Forms or paper questionnaires, as appropriate. This sheet includes demographic information such as age, sex, education level, occupation, perceived economic status, marital status, and religious beliefs, to be completed by the participant. The questionnaire also

includes items regarding the participant's prior musical training, frequency of daily music listening, motivations for listening, typical timing and methods of listening, and preferred activities during rest.

2. Leukemia-Related Treatment Data Sheet This data will be extracted from the patient's medical records by the researcher. It includes information on chemotherapy drugs and dosages, as well as laboratory values—specifically Absolute Neutrophil Count (ANC), Hemoglobin (Hb), and Albumin—from before chemotherapy (T0) and on Day 21 (T1).

3. Tang Fatigue Rating Scale (TFRS) While many reliable and valid fatigue scales exist globally, many have limitations. Considering that fatigue assessment should encompass physical, psychological, and activity dimensions, the TFRS was selected as the primary outcome measure for this study.

The TFRS contains 37 items across three subscales: Physical (15 items), Psychosocial (12 items), and Daily-Living (10 items). It uses a 10-point rating scale, where higher scores indicate greater fatigue severity. The TFRS underwent content validity testing by three PhD-level experts in fatigue theory and psychometrics. It was validated in a sample of 107 patients with chronic heart failure. The internal consistency (Cronbach's α) was 0.96 for the total scale, and 0.83 (Physical), 0.92 (Psychosocial), and 0.97 (Daily-Living) for the subscales. The TFRS demonstrated excellent validity: **convergent validity** with the Visual Analogue Scale for Fatigue (VAS-F) was 0.87, and **construct validity** with The Beck Depression Inventory-Second Edition (BDI-II) was 0.77 (Tang et al., 2010).

In the study by Tang et al. (2010), the TFRS also showed a significant positive correlation with the New York Heart Association (NYHA) functional class ($r = 0.75, p < 0.01$) and significant negative correlations with Ejection Fraction (EF) ($r = -0.46, p < 0.01$) and Hemoglobin (Hb) ($r = -0.27, p < 0.01$) (Tang et al., 2010).

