The laboratory data required for this study (WBC, Hb, Albumin) will be obtained by the researcher through a medical record review. Data from blood samples drawn as part of standard clinical care, taken before chemotherapy (T0) and on Day 21 (± 3 days) (T1), will be utilized. **No additional blood draws will be required for this study.**

Throughout the study period, participants may ask questions at any time via the official LINE group, and the researcher will provide responses.

Ethical Considerations

This study will be initiated only after obtaining approval from the Institutional Review Board (IRB) and securing consent from the nursing administrators and attending physicians of the recruitment site. Prior to formal enrollment, the researcher will personally explain the study's purpose, procedures, and methodology to each potential participant.

The researcher will address all participant inquiries. Participants will be explicitly informed that their participation is voluntary, that they may withdraw from the study at any time without penalty, and that their decision will not affect the quality of their medical treatment or nursing care in any way.

All research data collected from participants will be processed using anonymous coding. The data will be securely stored by the researcher and used exclusively for academic purposes. Confidentiality will be strictly maintained, and data will not be publicly disclosed or used for other purposes, ensuring the protection of participant privacy.

Data Processing and Statistical Analysis

1. Data Management The researcher will review all questionnaires for completeness. All collected data will be coded and entered into the Statistical Packages for the Social Sciences (SPSS) version 26.0 for data processing and management.

2. Statistical Analysis In accordance with the study's objectives, data analysis will be divided into descriptive and inferential statistics, as outlined in Table 3-3.

- **a. Descriptive Statistics:** Based on the characteristics of the variables, data

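### Control patients can listen to their own music and share a messaging group with music patients, but the plan describes no record of their listening after baseline, so dilution of the fatigue difference could not be seen

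*Combined protocol and SAP*

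**What the plan says.** - **Intervention.** Research Design: "Group A participants will listen to self-selected music in addition to receiving standard care"; Group B gets standard care alone. The Music Therapy Protocol sets 30 minutes once a day for 21 days, normally on the participant's own headphones. The Background describes music as something patients or relatives can deliver themselves.
- **Control instruction.** The plan describes nothing that Group B is told about its own music.
- **Shared channel.** Under Research Procedures, every participant is invited to the study's LINE group while baseline questionnaires are being completed; randomisation follows. During the study, "participants may ask questions at any time via the official LINE group", and the researcher answers.
- **Listening at baseline.** The demographic sheet, collected only at T0, asks both arms about "frequency of daily music listening" along with motives, timing, methods and preferred rest activities.
- **Listening after baseline.** The Music Therapy Protocol gives the diary's purpose as "to confirm adherence to the music therapy protocol in the experimental group". Both arms keep the diary for 21 days, but Research Procedures describes only the fatigue NRS for Group B. The Day 21 collection (TFRS, NRS, G-8, laboratory values) has no listening item.
- **Analysis.** GEE by intention to treat. No summary of music exposure is planned, and Sample Size Calculation makes no allowance for control listening.

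**The concern.** The contrast under test is music against no added music, but nothing in the plan protects or measures that contrast on the control side. Controls have the means. They also know what is being tested, because the purpose and methods are explained before consent and the T0 sheet asks about music. They are on the same ward as Group A, and the shared LINE group is one more route by which the idea could pass between arms.

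If music reduces fatigue, each control patient who listens moves the Group B mean toward that of Group A. The intention-to-treat difference then understates what music does compared with none. The sponsor's own literature review explains a null trial partly by too small a dose of music. This trial could not apply that reasoning to itself, because the difference in dose between its arms would be unknown. Daily listening that is not recorded at the time cannot be reliably recovered later.

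**Working it through.** **1. Reproducing the planned size.** Inputs from Sample Size Calculation: "a significance level (α) of 0.05", power 0.80, "effect size of 0.21". Its result: "This calculation yielded a required sample size of 34 participants". The metric, number of time points and within-patient correlation are not stated. Assuming Cohen's f, a repeated-measures group-by-time interaction, k = 2 groups, m = 4 times (the NRS schedule), correlation ρ = 0.5 and sphericity:

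- λ = f² × N × m / (1 − ρ) = 0.21² × 34 × 4 / 0.5 = 12.0
- df₁ = (k − 1)(m − 1) = 3; df₂ = (N − k)(m − 1) = 96
- power = 0.823, and 34 is the smallest even N that reaches 0.80.

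So 34 is reproduced with almost no reserve. With m = 2, the schedule of the TFRS (named as the primary outcome measure), λ = 6.0 and power at 34 is 0.66 before any dilution.

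**2. Dilution.** Let c be the share of controls who listen and g the fraction of the music effect they gain. The expected difference is multiplied by (1 − c × g). Neither c nor g is in the documents.

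- c = 25%, g = 1: 0.21 × 0.75 = 0.158
- c = 50%, g = 1: 0.21 × 0.50 = 0.105
- c = 50%, g = 0.5: the multiplier is 1 − 0.25 = 0.75, the same loss as in the first line.

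**3. Effect on any test that starts at 80% power** (two-sided α = 0.05, normal approximation). Power = Φ((1 − c × g) × (1.960 + 0.842) − 1.960).

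- Multiplier 0.75: Φ(2.101 − 1.960) = Φ(0.141) = 55.6%
- Multiplier 0.50: Φ(1.401 − 1.960) = Φ(−0.559) = 28.8%

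**4. The same idea in the model of step 1** (g = 1, ρ = 0.5).

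| Controls gaining full effect | Power at 34, m = 4 | N for 80% power, m = 4 | Power at 34, m = 2 |
|---|---|---|---|
| 0% | 0.82 | 34 | 0.66 |
| 10% | 0.73 | 40 | 0.57 |
| 20% | 0.61 | 50 | 0.48 |
| 30% | 0.49 | 66 | 0.38 |
| 50% | 0.27 | 126 | 0.22 |

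The 50% row (0.27) differs slightly from 28.8% in step 3 because it is a 3-df F test starting from 0.82.

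**5. What could be checked at the end of the trial.** Group A is assigned 30 × 21 = 630 minutes, and its diary is meant to confirm them. For Group B the plan describes no post-baseline figure to set beside that, so neither c nor the contrast in minutes could be estimated.

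**The case against.** The strongest reply is that the comparison is pragmatic. Usual care includes whatever music patients ordinarily play, habitual listening should be balanced by randomisation, and intention to treat validly estimates what assigning a daily scheduled session adds. Dilution also cannot create a false benefit. This stands. A reader might infer that a null result would be uninterpretable; the documents do not support that. It would answer the assignment question and leave open only whether music itself does nothing or the arms had too little contrast.

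Second, a reader might infer that controls will read music patients' messages, that allocation is revealed in the LINE group, or that the confidentiality undertaking is broken. The plan describes neither the visibility of messages nor that of membership, and joining is by invitation. The undertaking in Ethical Considerations concerns collected research data. What stands is only that one channel serves both arms and nothing separates them. How much it adds to what controls learn at consent is unknown.

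Third, the diary form is not shown and the consent pages were removed, so an item or instruction for controls may exist there. The supportable statement is that none is described. The T0 items would identify habitual listeners, and the covariate list is open-ended, so adjusting for habit is possible. But habit before chemotherapy does not measure listening during the 21 days.

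Finally, the power losses are hypothetical, since casual listening is not the scheduled dose. That is accepted; they show sensitivity and are not a forecast.

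**Conclusion.** The point holds as a gap in measurement and separation. Controls have the same means to listen, share a channel with Group A from before allocation, and have no described listening record after T0. If music works, the bias runs toward no difference. Its size is unknown. A 25% or 50% loss of the difference, taking 80% power to about 56% or 29%, assumes that this share of controls gains the full effect; lighter listening costs less. The 80% starting point is itself the planning figure and is reproduced only with four time points, so it does not describe the TFRS at two. The intention-to-treat estimate stays valid for assignment to scheduled music over usual care. This is a change worth making before enrolment because it is cheap and the exposure data cannot be rebuilt afterwards.

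**What to change.** 1. **Research Procedures, both mentions of the LINE group.** Replace the common group with one-to-one messages to the study account, or with a separate group per arm opened only after allocation.
2. **21-day diary, both arms.** Add one neutrally worded item: total minutes of music listened to today. In Group A, record study-session minutes separately, so that total and additional listening can both be derived. An item that left out study sessions would not show the full contrast between arms.
3. **Statistical Analysis.** Pre-specify a descriptive table of total daily listening minutes by arm, to be read alongside the intention-to-treat result. The primary comparison does not change.

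**Cost.** A messaging setting, one diary line (two in Group A) in a diary that both arms already keep at about one minute per entry, and one table. No extra patients, visits or blood draws. The downside is that asking about music may prompt a little listening in controls. Placing the item within a short list of rest activities, a topic the T0 sheet already covers, limits this.

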moderate positive correlation between WBC count and fatigue ($r = 0.63$, $p < 0.05$). However, other studies, including those on post-operative colorectal cancer patients and leukemia patients, reported no significant correlation between fatigue severity and WBC count ($\beta = -0.037$, $p = 0.588$; $\beta = 0.16$, $p = 0.29$, respectively) (Addisia et al., 2022; Wei & Li, 2018).

The possible reasons for these discrepant findings may relate to cancer type and stage. Different cancer types and stages necessitate different treatment dosages, leading to varying degrees of myelosuppression (Anand et al., 2023; Kuter, 2015). Furthermore, the timing of fatigue assessment is relevant. If assessed during chemotherapy, patients are likely experiencing side effects, including leukopenia. If survivors are assessed, the decrease in WBCs may be less pronounced. The week following chemotherapy is the period of peak side effects (Chen & Tang, 2020). Therefore, research designs should collect blood laboratory values concurrently with fatigue assessments during the patient's chemotherapy process to accurately monitor the fatigue problem. Study designs must reflect the clinical reality, synchronizing the collection of laboratory data and fatigue assessments to effectively capture the correlation between fatigue and WBC count.

2. Hemoglobin (Hb) According to the World Health Organization (WHO) and the American Association of Blood Banks (AABB), anemia is defined as $Hb < 12$ g/dl for females and < 13 g/dl for males (Lotterman & Sharma, 2022; Safiri et al., 2021). Anemia ($Hb < 12$ g/dl) can result from the cancer itself, treatments (chemo/radiotherapy), malnutrition, bone marrow infiltration, or hemorrhage (Madeddu et al., 2018; Wang et al., 2002). Chemotherapy side effects cause myelosuppression, inhibiting erythropoiesis (red blood cell production) (Jhamb et al., 2008; Thong et al., 2020). This leads to insufficient hemoglobin, which impairs systemic oxygen delivery and subsequently causes fatigue (Thong et al., 2020; Wang, 2008). While 0% to 67% of chemotherapy patients may develop anemia, some studies note that fatigue can occur even in non-anemic cancer patients (Gaston-Johansson et al., 1999).

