Prior to study commencement, approval will be obtained from the Institutional Review Board (IRB). Following IRB approval, and after explaining the study to and receiving consent from the attending physicians and ward nursing staff, the researcher will conduct participant recruitment in the inpatient wards and outpatient clinics. Individuals who meet the inclusion criteria will be identified as potential participants. The researcher will explain the study's purpose and methodology to these individuals. After obtaining informed consent and a signed consent form, the researcher will administer the pre-test (T0) questionnaires. This packet includes the Demographic Data Sheet, the Tang Fatigue Rating Scale (TFRS), the G-8 screening tool, and the symptom diary. This self-administration process is expected to take approximately 10 minutes. If a participant is unable or unwilling to self-report (e.g., due to advanced age or fatigue), the researcher will conduct a structured interview to complete the questionnaires, which is estimated to take 30–40 minutes. Concurrently, all participants will be invited to join the study's official LINE group for communication. Following the collection of baseline questionnaires, a computer-generated randomization sequence will be implemented by personnel not directly involved in the study (i.e., someone other than the principal investigator) to allocate participants to either the experimental group (Group A) or the control group (Group B). Participants in Group A, after confirming their chemotherapy infusion line is properly connected, will begin listening to 30 minutes of self-selected music while concurrently receiving standard care. Participants in Group B will receive standard care only. A total of **60 participants** with Acute Myeloid Leukemia (AML) undergoing chemotherapy are expected to be recruited (n=30 per group). Both groups will be required to complete the symptom diary throughout the 21-day

study period (est. 1 minute per entry). Group A will complete the Fatigue Numerical Rating Scale (NRS) immediately following each music therapy session. Group B will complete the Fatigue NRS 30 minutes after the commencement of their chemotherapy infusion.

On Day 21 (T1), the researcher will collect the post-test data (TFRS, NRS, and G-8) in the ward. If a participant has been discharged, data will be collected via telephone interview or an online questionnaire.

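### Planned chemotherapy regimen is recorded but not pre-specified as a covariate, which leaves chance imbalance unaddressed and gives up some precision in a small trial

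*Combined protocol and SAP*

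**What the plan says.** Research Setting and Participants requires AML, age 20 or older, and "Scheduled to receive initial (first-time) chemotherapy". No regimen is named or excluded. The Literature Summary speaks of conventional chemotherapy without defining it.

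Research Instruments, item 2 (Leukemia-Related Treatment Data Sheet), takes treatment data from the medical record: "It includes information on chemotherapy drugs and dosages, as well as laboratory values".

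Research Procedures states that "a computer-generated randomization sequence will be implemented by personnel not directly involved in the study". It gives no stratification factor, block size or minimisation.

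Sample Size Calculation says the analysis will control for baseline demographic and disease characteristics. Its examples are age, sex, education, occupation, perceived economic status, marital status, religious beliefs and metastasis. Regimen is not among them, but the list is introduced as examples.

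Data Processing and Statistical Analysis mentions chemotherapy drug names only among the categorical variables to be described by counts and percentages. Its GEE paragraph names no covariate.

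The literature review, under White Blood Cell Count, says that cancer types and stages "necessitate different treatment dosages, leading to varying degrees of myelosuppression".

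**The concern.** Fatigue, white cells, hemoglobin and albumin at Day 21 are all measured after chemotherapy has begun. The protocol's own review links treatment intensity to myelosuppression, and chemotherapy side effects to fatigue and to low blood values. If patients receive different first regimens, regimen is a plausible prognostic factor for every outcome.

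T0 is taken before chemotherapy, so adjusting for the T0 value does not remove a regimen difference that arises afterwards. With 22 per arm (or 30, the other recruitment figure in the protocol), chance can leave the arms unlike in regimen. Any variation due to regimen also stays in the error term. The plan collects the data needed to deal with both, yet names factors such as religion and marital status instead.

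**Working it through.** **1. The plan's own sample size.** Inputs from Sample Size Calculation: "a significance level (α) of 0.05, statistical power ($1-\beta$) of 0.80", an "effect size of 0.21" of unstated type, and "a potential attrition rate of 30" per cent. I read 0.21 as Cohen's f in a repeated-measures group-by-time F test. The number of time points m = 4 and the correlation ρ = 0.5 are assumptions.

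- λ = f²·N·m/(1−ρ) = 0.0441 × 34 × 4 / 0.5 = 12.0, with 3 and 96 degrees of freedom. Power is 0.823, so the stated 34 is reproduced ("This calculation yielded a required sample size of 34 participants").
- 34 × 1.30 = 44.2, which matches the stated 44.

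The sizes to examine are therefore 17 per arm (34 in all), 22 per arm (44) and 30 per arm (60, from Research Procedures).

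**2. Chance of imbalance.** The documents give no regimen mix. Assume two classes, with share p in the less common one and equal arms. The counts in the two arms are independent Binomial(n, p). Exact probability that the shares differ by at least 20 points:

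| n per arm | Smallest qualifying difference | p = 0.2 | p = 0.3 | p = 0.4 |
|---|---|---|---|---|
| 17 | 4/17 = 23.5 points | 13.0% | 18.9% | 22.0% |
| 22 | 5/22 = 22.7 points | 8.8% | 13.7% | 16.5% |
| 30 | 6/30 = 20.0 points | 7.5% | 12.0% | 14.7% |

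At 22 per arm with p = 0.1 the chance is about 2%.

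**3. What such an imbalance does.** Shift in the arm difference = g × (difference in shares), where g is the regimen effect in within-class SDs, assumed 0.5 to 1.0.

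- g = 0.5: 0.5 × 0.20 = 0.10 SD.
- g = 1.0: 1.0 × 0.20 = 0.20 SD.

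As a benchmark take a true effect of 2f = 0.42 SD (assumed). The shifts are then 0.10/0.42 = 24% and 0.20/0.42 = 48% of it.

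At 22 per arm and g = 1.0, with class shares of 60% and 40% in the two arms:

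- The within-arm variance is 1 + 0.24, so the standard error used by the unadjusted test is √(1.24 × 2/22) = 0.336.
- The critical difference is 2.018 × 0.336 = 0.678.
- Given the imbalance, the estimate varies with standard error √(2/22) = 0.302.
- Power for 0.42 SD is about 20% with no imbalance, 42% if the imbalance favours music and 7% if it goes against music.
- The false-positive rate given that imbalance is 6%.

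**4. Averaged over all randomisations.** Simulation with 20,000 runs per setting, classes 50/50, comparing the arms without and with regimen in the model:

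| N | g | Power for 0.42 SD, unadjusted | Power for 0.42 SD, adjusted | Type I error, either way |
|---|---|---|---|---|
| 44 | 0.5 | 26% | 27% | about 5% |
| 44 | 1.0 | 23% | 27% | about 5% |
| 60 | 0.5 | 35% | 36% | about 5% |
| 60 | 1.0 | 30% | 36% | about 5% |

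**5. How regimen must enter the model.** In a GEE with T0 and T1 both as outcomes, the treatment effect is the arm difference in change. A regimen main effect adds the same amount at T0 and T1 and cancels from the change. Only a regimen-by-time term, or a model for T1 with T0 and regimen as covariates, adjusts for what regimen does after T0.

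**The case against.** The strongest reply is that randomisation already covers this. Chance imbalance in any one factor is part of the test's error rate, and step 4 confirms it. A reader might infer that an unbalanced regimen biases the trial or inflates false positives. The documents do not support that: overall type I error is about 5% with or without adjustment, and about 6% even given a 20-point imbalance in the setting of step 3. In these scenarios an imbalance is more likely to hide an effect than to imitate one.

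A reader might also infer that the analysis cannot correct for regimen. It can: the covariate list is open and refers to disease characteristics. Nor does its place among the described variables show that regimen is excluded from the model, since sex, education, occupation and religion are described there and are also named as covariates. What stands is that regimen is not pre-specified, so its use would be decided later.

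Nothing in the documents makes regimen the strongest influence on the outcomes. The sentence on dosage and myelosuppression explains differences between cancer types and stages, whereas this trial enrols one disease at first treatment. If one regimen dominates, the problem nearly disappears.

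One could also apply 30% loss to 22 per arm (22 × 0.7 = 15.4) and report 32-35% at 15 per arm. That is mostly a grid effect: 3/15 is exactly 20 points. At 16 per arm, where four patients are needed, the figure is 17.5-20.6%.

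Finally, stratified allocation is not clearly better. In an open trial on one ward, small blocks within strata make the next assignment easier to guess. That objection stands.

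**Conclusion.** The point holds as an incomplete covariate specification. Regimen is free to vary, plausibly prognostic, acts after baseline and is already collected, yet the named covariates leave it out. The consequence is some lost precision and an unaddressed chance imbalance, not systematic bias.

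Its size is modest. With 30-40% of patients in the less common class, a 20-point imbalance has a chance of about 14-17% at 22 per arm, 12-15% at 30 and 19-22% at 17, and it would move the contrast by 0.10-0.20 SD. The average power gain from adjustment at N=44 is 1 to 4 percentage points. The two-class split, the class shares, the 0.5-1.0 SD regimen effect and the 0.42 SD benchmark are all assumptions. A dominant regimen or a weak regimen effect would make the gain negligible.

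**What to change.** In Sample Size Calculation and in Data Processing and Statistical Analysis, pre-specify planned regimen class as a covariate in the GEE for fatigue and for each blood value. Use two levels, defined before the first patient is randomised. Assign each patient's class before allocation from the scheduled order, not from what was later given, because treatment received is a post-randomisation variable. Enter it so that it can act on change: as a class-by-time term, or beside T0 in a model for T1. Let it replace a weak demographic item such as religion or marital status, so that the model does not grow at this sample size.

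The cost is one field completed before allocation and one changed line in the model. No patients, visits or blood draws are added. The downside is that the gain may be small.

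Stratifying the sequence by the same class is optional. If it is considered, weigh it against the easier guessing of the next assignment in an open single-ward trial. The covariate alone secures most of the benefit and remains available if allocation has begun, provided the planned class can be established from orders dated before allocation.
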